7.1.2. Efficacy evaluation criteria

The primary and secondary efficacy endpoints of SHR-1210 in combination with apatinib mesylate in the treatment of advanced mucosal malignant melanoma will be evaluated according to RECIST v1.1.

The lesions identified at baseline should be examined every 2 cycles during the first 12 treatment cycles (bone scans should be performed when there is suspicion of bone progression or when confirming a CR), and every 3 cycles thereafter. This schedule is not affected by interruptions or delays in treatment. If new lesions are suspected, timely examinations can be performed. The first PR or CR must be confirmed 4 weeks \pm 7 days later. If disease progression is observed according to RECIST 1.1, imaging examinations should be performed 4 ~ 6 weeks later for confirmation (except for rapid progression and significant clinical progression).

Survival records and assessment: After the treatment withdrawal, the subjects will be

followed up once a month for survival status via telephone, until death, loss to follow-up, withdrawal of informed consent, or termination of the study. The evaluation of tumor response will involve all known or suspected sites of lesions.

Radiological imaging examinations include CT scans or MRI scans of the chest, abdomen, or pelvis; brain CT or MRI scan is used for subjects with known or suspected brain metastases; bone scan is used for subjects with known or suspected bone metastases (see section 7.1 for details on imaging examinations).

If the overall health condition of a subject deteriorates, requiring discontinuation of the medication, but there is no objective evidence of disease progression at this time, it should be reported as symptomatic worsening.

If no imaging examination has been performed within 4 weeks before the end of treatment, an imaging examination should be conducted at the end of the study treatment or upon withdrawal from the study for efficacy evaluation. For patients with non-imaging evidence of progression (intolerable, other circumstances), tumor assessments should be performed every 3 months until disease progression, death, or initiation of other anti-tumor treatments.

7.2. Safety evaluation

7.2.1. Adverse events

The incidence and severity of AEs and SAEs will be assessed according to the National Cancer Institute (NCI) - Common Terminology Criteria for Adverse Events (CTCAE) V4.03 criteria.

Dose interruption rate and dose discontinuation rate due to AEs will be calculated.

7.2.2. Laboratory safety evaluation

All laboratory abnormalities with clinical significance or meeting the definitions of AE/SAE should be recorded in the CRF:

In the report, investigators should use clinical terms as much as possible instead of laboratory terms (such as anemia, rather than low hemoglobin value).

7.2.3. Vital signs, physical examination, and body weight measurement

Vital signs and physical examinations and body weight measurement will be performed according to the study schedule.

During the screening period, a comprehensive physical examination must be conducted, and all examination results must be recorded in the CRF.

During the study, a comprehensive physical examination must be conducted, and only abnormal findings should be recorded in the CRF. If there is no change compared with the screening period, there is no need to repeat the recording.

7.3. Biomarkers evaluation

This study will investigate the relationship between the expression level of PD-L1 in tumor tissue and/or peripheral blood samples collected at baseline, the proportion of positive cells, and/or other biomarkers, such as baseline TMB, and the therapeutic efficacy.

8. Adverse Events Reporting

8.1. Adverse events (AEs)

8.1.1. Definition of AEs

AEs refer to untoward medical events that occur in clinical subjects after receiving a drug, but do not necessarily have a causal relationship with the treatment. In this study, AEs will be collected from the time the subject signs the ICF until at least 30 days after the last administration of the drug. It is required to follow up and collect SAEs and irAEs within 90 days after the last administration of SHR-1210. If the patient starts a new anti-tumor treatment, follow-up will be performed until the initiation of the anti-tumor treatment (if it starts within 30 days after the last administration,

follow-up will be performed until at least 30 days after the last administration of SHR-1210; if it starts after 30 days, follow-up will be performed until the initiation of the anti-tumor treatment). AEs can be any unfavorable and unexpected symptoms, signs, laboratory abnormalities, or diseases, including the following situations:

- 1) Worsening of pre-existing (prior to entering the clinical study) medical conditions/diseases (including aggravation of symptoms, signs, and laboratory abnormalities);
- 2) Newly occurring AEs: Any newly occurring adverse medical conditions (including symptoms, signs, newly diagnosed diseases);
- 3) Abnormal laboratory test values or results with clinical significance that are not caused by concomitant diseases.

Investigators should document any AEs experienced by the subjects in detail, including: description of the AEs and all related symptoms, onset time, severity, cause, relationship to the study drug, duration, measures taken, final results and outcome.

8.1.2. Criteria for AE severity

Refer to the NCI-CTCAE 4.03 version for the grading criteria of drug-related AEs. If an AE not listed in the NCI-CTCAE 4.03 version table occurs, refer to the following criteria:

Table 2 Criteria for AE Severity

Grade	Clinical Description of Severity
1	Mild; asymptomatic or minor clinical symptoms; only clinical or laboratory abnormalities; no treatment required.
2	Moderate; requiring minor, local, or non-invasive treatment; limitations in age-appropriate instrumental activities of daily living (ADL); instrumental ADL refer to cooking, shopping, making phone calls, and counting money,

	etc.
3	Severe or medically serious symptoms but not immediately life-threatening; leading to hospitalization or prolongation of hospitalization; disability; limitations in self-care ADL. Self-care ADL refer to bathing, dressing, undressing, feeding self, using the toilet, taking medications, etc., and not being bedridden.
4	Life-threatening; urgent treatment indicated
5	Leading to death

8.1.3. Assessment of the relationship between AEs and study drugs

The possible causality between the AE and the study drug should be assessed using a five-level classification system: "Definitely related," "Possibly related," "Doubtfully related," "Not related," and "Unable to determine". The AEs with the causalities of "Definitely related," "Possibly related," and "Unable to determine" are all considered as adverse drug reactions. When calculating the incidence of AEs, the total number of subjects involved in the three categories will be used as the numerator, and the total number of subjects for safety evaluation will be used as the denominator.

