Study Endpoints	
Primary Study Endpoints
 
Assessed ORR per Response Evaluation Criteria in Solid Tumors (RECIST) 1.1 criteria
 
Secondary Study Endpoints
 
Efficacy:
 
Assessed PFS per RECIST 1.1 criteria
 
 * Time to response (TTR) * Duration of response (DOR) * Disease control rate (DCR) * 6-month survival rate * 9-month survival rate * 12-month survival rate * Overall survival (OS)

	
Safety
 
 * Incidence and severity of adverse events (AEs) and serious adverse events (SAEs), abnormal laboratory values, determined according to the National Cancer Institute (NCI) - Common Terminology Criteria for Adverse Events (CTCAE) V4.03criteria * Dose interruption rate, dose discontinuation rate due to AEs 
Exploratory Study Endpoints
 
 * To explore the relationship between programmed cell death ligand-1 (PD-L1) expression level, proportion of positive cells, and/or other biomarkers, such as tumor mutation burden (TMB) at baseline, and efficacy * To explore the correlation between biomarkers in archived and/or fresh tumor tissue and blood samples and disease progression * To evaluate the quality of life in patients with advanced mucosal melanoma treated with SHR-1210 in combination with apatinib mesylate

Study Subjects
	
 1. Patients with advanced mucosal malignant melanoma ineligible for radical surgery 2. Patients with advanced mucosal malignant melanoma experiencing recurrence and metastasis after radical surgery of the primary lesion

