Statistical Analysis	
The main results of this study will be presented using descriptive statistical methods. The mean, standard deviation, median, maximum, and minimum values will be listed for measurement data, while the frequency (proportion), rate, and confidence interval (CI) will be listed for counting data and ranking data. All statistical analyses will be programmed and calculated using SAS 9.4 or above.
 
 ● Safety Analysis: 
The descriptive statistical analysis will be used for analyzing AEs, SAEs, and adverse reactions (adverse reactions are defined as AEs with the causality to the study drug as "definitely related/possibly related/not evaluable") occurring in various populations. The worst clinical grade will be described for the laboratory test results at baseline and post-baseline.
 
 ● Efficacy Analysis: 
The point estimates will be performed for efficacy endpoints such as ORR and DCR, and their 95% CIs will be provided. The interval estimates will be performed using the Clopper-Pearson

	
method.
 
PFS, DOR, OS, 6-month, 9-month and 12-month survival rates will be estimated using the Kaplan-Meier method, and 95% CIs will be calculated. TTR will be described using mean, standard deviation, median, maximum, and minimum values.
 
● Additional Analyses: 
For the SHR-1210-related solid tumor biomarkers, such as PD-L1 or other biological markers levels in tumor tissues, descriptive statistics will be used for analysis.

--	--

List of Abbreviations and Related Terms

Acronyms / Abbreviations	Explanation
ADA	Anti-drug antibody
ADR	Adverse drug reaction
AE	Adverse events
ALP	Alkaline phosphatase
ALT (SGPT)	Alanine aminotransferase
APTT	Activated partial thromboplastin time
AST (SGOT)	Aspartate aminotransferase
ANC	Absolute neutrophil count
AUC	Area under the concentration-time curve
BUN	Blood urea nitrogen
CBC	Complete blood count
Cl ⁻	Chlorine
CRP	C-reactive protein
CT	Computer-assisted tomography
CTCAE	Common Terminology Criteria for Adverse Events
DLT	Dose limiting toxicity
DSMB	Data and Safety Monitoring Board
EC	Ethics Committee
ECG	Electrocardiogram
ECOG	Eastern Cooperative Oncology Group

CRF	Case report form
EDC	Electronic data capture
FAS	Full analysis set
CFDA	China Food and Drug Administration
GCP	Good Clinical Practice
GLP	Good Laboratory Practice

HIV	Human immunodeficiency virus
IC	Informed consent

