8.2.3. Disease progression

Disease progression is defined as the worsening of the patient's condition caused by the investigational drug targeting the primary tumor, including radiographic progression and the progression of clinical symptoms and signs. The emergence of new metastatic lesions relative to the primary tumor, or the progression of existing metastatic lesions, are considered as disease progression. It will be not reported as an SAE for the events that are life-threatening due to the symptoms and signs of disease progression, requiring hospitalization or prolongation of hospitalization, or lead to permanent or serious disability/incapacity/impairment of work capacity, congenital anomaly, or birth defect. It will be reported as an SAE for deaths caused by symptoms

and signs of disease progression.

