10.5.4. Safety analysis

The descriptive statistical analysis will be used for analyzing AEs, SAEs with \geq CTCAE grade 3, and adverse reactions (adverse reactions are defined as AEs with the causality to the study drug as "definitely related/possibly related/not evaluable"), adverse reactions with \geq CTCAE grade 3, AEs leading to dose modifications occurring in population in each dose group. The worst clinical grade will be described for the laboratory test results at baseline and post-baseline.

Additionally, the summary analysis of AEs mentioned above is also applicable for each category of immune-related AEs, including immune-related pneumonia, immune-related enteritis, immune-related thyroid dysfunction, immune-related nephritis and renal failure, immune-related hypophysitis, and other immune-related adverse reactions.

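### Section 8.1.3 builds AE incidence from the adverse-drug-reaction categories only, and 10.5.4 limits the SAE summary to grade 3 or higher, against the protocol's own definitions and safety endpoint

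*Protocol*

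**What the plan says.** Section 8.1.3 grades causality as definitely related, possibly related, doubtfully related, not related, or unable to determine. The first two and the last "are all considered as adverse drug reactions". The next sentence gives the only AE-incidence formula in the protocol: "When calculating the incidence of AEs, the total number of subjects involved in the three categories will be used as the numerator". Its denominator is everyone evaluated for safety.

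Other sections treat AEs as all-causality:

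- Section 8.1.1 defines AEs as untoward events after receiving a drug that occur "but do not necessarily have a causal relationship with the treatment".
- The safety endpoint in the synopsis is "Incidence and severity of adverse events (AEs) and serious adverse events (SAEs), abnormal laboratory values". It carries no causality limit, and neither does section 7.2.1.
- The synopsis (Statistical Analysis) says: "The descriptive statistical analysis will be used for analyzing AEs, SAEs, and adverse reactions". AEs and adverse reactions are separate items there.
- Section 10.5.4 also separates the two, but it opens: "The descriptive statistical analysis will be used for analyzing AEs, SAEs with", followed by a threshold of CTCAE grade 3 or higher. The synopsis has no such threshold for SAEs.

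Section 8.2.3 describes progression as worsening of the patient's "condition caused by the investigational drug targeting the primary tumor". It takes non-fatal serious events due to progression out of SAE reporting and names congenital anomaly and birth defect among them.

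**The concern.** The protocol fixes a numerator for AE incidence, and it is the numerator of a different quantity. Anyone programming the tables from 8.1.3 would produce the adverse-reaction rate under the heading of AE incidence. Whether an event counts would then depend on a causality judgement made without blinding, in a study with no control arm and two active drugs. The endpoint is meant to be free of that judgement.

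The SAE mismatch is smaller but of the same kind. Seriousness and grade are different attributes. A summary of SAEs at grade 3 or higher does not deliver the endpoint, which is the incidence of SAEs.

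**Working it through.** The protocol states no AE rate, so there is no figure to reproduce. The check compares the sections and then applies simple arithmetic.

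**1. Which events enter each quantity**

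| Causality level (8.1.3) | AE by 8.1.1 | AE incidence by 8.1.3 | Adverse reaction by 8.1.3 |
|---|---|---|---|
| Definitely related | yes | yes | yes |
| Possibly related | yes | yes | yes |
| Unable to determine | yes | yes | yes |
| Doubtfully related | yes | no | no |
| Not related | yes | no | no |

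The last two columns are identical. Under 8.1.3, AE incidence and adverse-reaction incidence are the same number, so the separate summaries in the synopsis and 10.5.4 would duplicate each other. Section 10.5.4 gives no numerator of its own and so does not override 8.1.3. (The synopsis and 10.5.4 call the fifth level not evaluable, where 8.1.3 says unable to determine; the terms should be aligned.)

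**2. Size of the shortfall**

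Inputs: n = 30 planned patients (section 10.1), all assumed to be in the safety set; k = number of patients whose only events of the kind being counted are judged doubtfully related or not related. The documents give no value for k, so its range is an assumption.

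Shortfall = all-causality incidence − incidence by 8.1.3 = k/n.

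- k = 0: 0/30 = 0 points
- k = 1: 1/30 = 3.3 points
- k = 3: 3/30 = 10 points
- k = 6: 6/30 = 20 points

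For the rate of any AE, k counts only patients all of whose AEs fall in the two excluded levels. For a single event term, k counts patients whose only events of that term were so judged. For a given data set, k for one term can therefore be positive even when k for any AE is zero.

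**3. SAEs**

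Section 8.2.1 defines an SAE by outcome (death, threat to life, hospitalization, disability, birth defect, other significant events) and not by grade. A grade 2 event that requires hospitalization is an SAE. It belongs in the synopsis summary of SAEs but falls outside the SAE summary in 10.5.4. Pregnancy and overdose, which 8.2.1 gives as examples of significant events, also need not reach grade 3.

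**4. Progression wording**

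Read literally, the definition in 8.2.3 covers worsening that the drug causes. The next sentence describes progression by new or growing metastatic lesions, and deaths from progression stay reportable as SAEs. Section 8.2.1 lists congenital anomaly and birth defect as SAEs without exception, whereas 8.2.3 lists them among the exempt consequences of progression.

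**The case against.** The best defence is that 8.1.3 contains a labelling slip. The sentence stands in the causality section, directly after adverse drug reactions are defined by the same three levels, so AEs may have been written where adverse drug reactions was meant. The synopsis and 10.5.4 plan the two summaries separately, all AEs are recorded with their causality (8.1.1), and detailed summary methods are left to the SAP (10.2). Much of this stands: no data are lost, and an under-count arises only if 8.1.3 is followed. But the text as written still prescribes the wrong numerator. Section 10.2 itself says that SAP revisions touching endpoint definitions or their analyses should also appear in an amended protocol.

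On SAEs, 10.5.4 lists AEs without a grade limit, so a lower-grade serious event would still appear among the AEs. Table 2 also puts hospitalization at grade 3, but only for events that CTCAE does not list. The effect may be small; the contradiction remains.

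Two stronger inferences are tempting and are not supported:

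- A reader might infer from 8.2.3 that drug-caused serious events escape SAE reporting. The clause reads as a misplaced modifier beside tumor-based text. The exemption turns on symptoms and signs of progression, deaths remain reportable, and nothing there prevents recording the event as an AE. Loss of drug-toxicity SAEs is not shown.
- A reader might infer that leaving hepatitis out of the immune-related categories named in 10.5.4 shrinks the counts, since 9.1 lists it. The list is open and ends with a catch-all for other immune-related reactions, so these events are still counted.

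**Conclusion.** The contradiction is real. The protocol's only AE-incidence formula yields adverse-reaction incidence and conflicts with the AE definition, the safety endpoint and the separate summaries. If it is applied, the reported rate falls below the all-causality rate by 3.3 points per affected patient, assuming 30 patients in the safety set; the total depends on an unknown k and may be zero. The grade limit on SAEs in 10.5.4 also contradicts the synopsis; the documents do not allow its effect to be sized. The wording of 8.2.3 is a matter for clean-up. The finding is a rule that is wrong as written, not a demonstrated under-count of the safety endpoint.

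**What to change.** - **8.1.3:** State that AE incidence is the number of subjects with the event, regardless of causality, divided by the safety analysis set defined in 10.3. Label the three-category rate adverse drug reaction incidence and report it separately. Use one name for the fifth causality level throughout.
- **10.5.4:** Tabulate all SAEs of any grade, with grade 3 or higher as a subset, in line with the synopsis.
- **8.2.3:** Reconcile the causal clause in the definition of progression with the tumor-based text that follows it, and reconcile the birth-defect wording with the SAE definition in 8.2.1.

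The cost is a wording amendment. Section 8.1.1 already requires every AE to be documented with its relationship to the study drug, so no new data are needed. Reported AE rates would be equal to or higher than those from the present 8.1.3 rule.

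### Section 8.1.3 labels the incidence of adverse drug reactions as the incidence of AEs, which contradicts the all-causality AE endpoint

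*Protocol*

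**What the plan says.** The Protocol Synopsis (Study Endpoints, Safety) sets this secondary safety endpoint: "Incidence and severity of adverse events (AEs) and serious adverse events (SAEs), abnormal laboratory values". Section 7.2.1 repeats it: "The incidence and severity of AEs and SAEs will be assessed according to the National Cancer Institute". Neither place restricts the events by causality. Section 8.1.1 defines AEs as events that "do not necessarily have a causal relationship with the treatment".

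Section 8.1.3 sets out the five causality levels and assigns definitely related, possibly related and unable to determine to adverse drug reactions. Doubtfully related and not related fall outside. The next sentence fixes the calculation: "When calculating the incidence of AEs, the total number of subjects involved in the three categories will be used as the numerator". Its denominator is everyone evaluated for safety.

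The synopsis (Statistical Analysis, Safety Analysis) says: "The descriptive statistical analysis will be used for analyzing AEs, SAEs, and adverse reactions". Section 10.5.4 likewise names AEs and adverse reactions as separate items. Both attach the three-category definition to adverse reactions only. Section 10.3 assigns the Safety Analysis Set to the safety analysis.

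**The concern.** The three categories in the numerator sentence can only be the three just classed as adverse drug reactions. The sentence therefore describes one quantity and names another. It is also the only place in the protocol that says which subjects enter the numerator for AE incidence, so someone programming the safety tables from the protocol could reasonably take it as the formula.

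The distinction matters here because the trial is single-arm and open-label. The investigator records each event's relationship to study drug, with no control group to inform that judgement. An all-causality AE rate does not depend on the judgement; a rate limited to three causality levels does. At stake is whether a named secondary endpoint is reported as the quantity its name and definition promise.

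**Working it through.** The protocol states no AE rate, so there is no figure of its own to reproduce. The check is a comparison of passages, followed by arithmetic for scale.

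**1. Passages side by side**

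| Place in the protocol | Quantity | Causality limit |
|---|---|---|
| Synopsis, Study Endpoints | Incidence and severity of AEs and SAEs | None |
| 7.2.1 | Incidence and severity of AEs and SAEs | None |
| 8.1.1 | Definition of an AE | Causal link not required |
| 8.1.3 | Named as incidence of AEs | Three of five levels |
| Synopsis, Safety Analysis; 10.5.4 | AEs | None |
| Synopsis, Safety Analysis; 10.5.4 | Adverse reactions | Three of five levels |

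The synopsis and 10.5.4 call the third level not evaluable where 8.1.3 says unable to determine; I take these to be the same level. On that reading, the numerator in 8.1.3 matches the adverse-reaction row exactly and no AE row.

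**2. Effect of the rule**

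Let N be the number of subjects evaluated for safety, A the number with at least one AE of any causality, and U the number of those whose events are all rated doubtfully related or not related.

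- All-causality incidence: A/N
- Incidence under 8.1.3: (A − U)/N
- Difference: U/N, which is never negative and is zero only when U = 0

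A subject with one qualifying event and one unrelated event still counts towards overall incidence. For a single AE term, the same formula applies with A and U counted for that term.

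**3. Scale**

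Section 10.1 plans 30 patients. Assuming all enter the safety evaluation, N = 30 and each subject counted in U costs 1/30 = 3.3 percentage points.

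The counts below are assumed, because the documents give none. Intervals are Clopper-Pearson 95%.

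Any AE, with A = 24:

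| U | (A − U)/N | Incidence | 95% CI |
|---|---|---|---|
| 0 | 24/30 | 80.0% | 61.4 to 92.3 |
| 2 | 22/30 | 73.3% | 54.1 to 87.7 |
| 6 | 18/30 | 60.0% | 40.6 to 77.3 |
| 12 | 12/30 | 40.0% | 22.7 to 59.4 |

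One AE term, with A = 12:

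| U | (A − U)/N | Incidence | 95% CI |
|---|---|---|---|
| 0 | 12/30 | 40.0% | 22.7 to 59.4 |
| 3 | 9/30 | 30.0% | 14.7 to 49.4 |
| 6 | 6/30 | 20.0% | 7.7 to 38.6 |

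The first row of each table is the case in which the rule changes nothing.

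**The case against.** The strongest reply is that this is a slip of terminology and not an analysis decision. The sentence sits in a section on causality, directly after the definition of adverse drug reactions, and putting that term in place of AEs makes the whole protocol consistent. The wording is loose elsewhere too: the abbreviation list expands ICH and MedDRA incorrectly. Safety is a secondary, descriptive endpoint with no hypothesis or decision rule attached to the rate. Section 10.2 leaves detailed summary methods to an SAP that is not at hand.

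Most of this stands, and it limits the consequence. A reader might infer that no all-causality AE incidence would be reported, or that the AE and adverse-reaction lines would be the same number. The documents do not support that. The synopsis and 10.5.4 already list AEs separately from adverse reactions, nothing gives 8.1.3 precedence over them, and 8.1.1 requires AEs to be recorded with their relationship to study drug, so the all-causality rate can always be computed. Nor is it accurate to say that 8.1.3 counts only drug-related events, since unable to determine is included. The sentence does not mention SAEs, so it does not redefine that half of the endpoint.

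The reply does not remove the contradiction. The protocol does not leave the numerator open for the SAP; it fixes it, and the text conflicts with its own endpoint. Section 10.2 also requires that an SAP revision touching endpoint definitions or their analyses be reflected in an amended protocol.

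**Conclusion.** The point holds as an internal contradiction, probably of wording: the numerator in 8.1.3 gives the incidence of adverse drug reactions, while the endpoint, the AE definition and the safety analysis text call for AEs regardless of causality. Followed literally, the rule understates AE incidence whenever at least one subject has only events rated doubtfully related or not related, and leaves it unchanged otherwise.

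The firm figure is 3.3 points per such subject, given 30 subjects evaluated for safety. The larger drops shown are illustrations on assumed counts, not predictions. This should be fixed, but it does not threaten the trial: the data survive, the endpoint is descriptive, and the intended reading can be recovered from the rest of the protocol.

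**What to change.** Make two changes in 8.1.3:

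1. In the numerator sentence, replace *incidence of AEs* with *incidence of adverse drug reactions*.
2. Add a sentence such as: *AE incidence counts every subject in the Safety Analysis Set with at least one AE, regardless of causality.*

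Section 10.5.4 needs no change on this point, since it already lists AEs and adverse reactions separately. If an SAP exists, its AE numerator should be checked against the corrected text.

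The cost is one reworded sentence and one added sentence in a protocol amendment. No new data, visits or patients are needed. Compared with a literal application of 8.1.3, reported AE incidence will be higher or the same, depending on whether any subject has only excluded events.
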